7.2. Treatment Assignment

This is a single arm real-world study. All screened subjects who sign the informed consent form (ICF) and satisfied with all the key criteria will be considered enrolled.

7.2.1. Target and Non-target Lesions

The pulmonary vein isolation for treatment of PAF will be the target lesion. Ablation of the CTI may be performed with any approved catheter in subjects who manifest typical AFL during a procedure or subjects who have inducible typical flutter. The order to ablate will be decided by the operator based on the patient condition.

7.3. Justification for the Study Design

The study device, FARAPULSE Pulsed Field Ablation system has got CE mark and accumulated amount of clinical safety and effectiveness data. The ongoing ADVENT study, a prospective multicenter randomized control study, is powered for non-inferior safety and effectiveness margin, which will produce more clinical data. Boston Scientific China asserts that this real-world study with about 30 cases is reasonable to obtain local data to support FARAPULSE Pulsed Field Ablation system registration in China.

7.4. Method to control biases

This is a real-world study. Selection of patients will be made from the Investigational site's routine patients. All patients meeting the key eligibility criteria and having signed the ICF will be eligible for enrollment in the study. Control and reduction of potential bias associated with

a single-arm study design have been taken into account by defining key inclusion and exclusion criteria to represent a population similar to the patients with AF ablation in the real world, and defining a mITT set with population similar to the subjects enrolled in ongoing ADVENT trial and other trial about AF ablation.

Every effort will be undertaken to minimize missing or incorrect data. However, some missingness is inevitable. The reasons for missing or incorrect data will be described in detail and evaluated for assessment of possible bias if appropriate.

8. Subject Selection

8.1. *Study Population and Eligibility*

Subjects enrolled in the REPLACE study will be clinically indicated for an ablation procedure for the treatment of symptomatic, recurrent PAF with Class I or IIa recommendations according to 2018 Chinese expert consensus statement on atrial fibrillation therapy. Subjects must meet the key inclusion/exclusion criteria as outlined below in **Section 8.2** and **8.3**. Subjects assigned to modified ITT set must meet all the key criteria and additional criteria as outlined below in **Section 8.3**. The subjects selected for participation will be from the investigational site's general patient population. The investigator or its designee has the responsibility for screening all potential subjects and selecting those who meet study eligibility criteria.

8.2. *Inclusion Criteria*

Subjects who meet all of the following criteria (see **Table 8.2-1**) may be given consideration for inclusion in this clinical investigation, provided no exclusion criterion (see **Section 8.3**) is met.

Table 8.2-1: Inclusion Criteria

Key Inclusion Criteria	
1. Subjects who are ≥ 18 and ≤ 75 years of age on the day of enrollment;2. Subjects whose preoperative diagnosis is PAF confirmed by the clinician;3. De novo ablation procedure for PAF with Class I or IIa recommendations* according to 2018 Chinese expert consensus on atrial fibrillation therapy;4. Subjects who are able and willing to provide the defined observational data and/or participate in baseline and follow-up evaluations for the full study;5. Subjects who are willing and capable of providing informed consent. 
* In 2018 Chinese expert consensus on atrial fibrillation therapy, subjects with recurrent, symptomatic PAF and refractory or intolerant to at least one class I or class III antiarrhythmic medication are recommended to accept ablation therapy under Class I recommendation; Subjects with recurrent, symptomatic PAF are recommended to accept ablation therapy as the first line therapy under Class IIa recommendation.

-------------------------------	--

8.3. Exclusion Criteria

Subjects who meet any one of the following key exclusion criteria in **Table 8.3-1** cannot be included in this study or will be excluded from this clinical study. No vulnerable populations will be enrolled in this study. See **Section 25.2** for the definition of a vulnerable subject. Subjects who meet any one of the following additional exclusion criteria in **Table 8.3-1** cannot be included in the mITT set or will be excluded from mITT set.

Table 8.3-1: Exclusion Criteria

Key Exclusion Criteria	
 1. Subjects who, in the judgment of the investigator, have a life expectancy of less than one year before the procedure; 2. Women of childbearing potential who are, or plan to become, pregnant during the time of the study; 3. Subjects with any known contraindication to AF ablation with FARAPULSE Pulsed Field Ablation system, anticoagulation therapy, or contrast media in the judgment of the investigator or subjects unwillingness to use systemic anticoagulation 4. Subjects who are currently enrolled in another investigational study or registry that would directly interfere with the current study.
Additional Exclusion Criteria for mITT set	
 1. AF that is any of the following: 
 • Persistent (both early and longstanding) by diagnosis or continuous duration > 7 days • Requires four or more direct-current cardioversions in the preceding 12 months before the procedure. • Secondary to electrolyte imbalance, thyroid disease, alcohol or other reversible/ non-cardiac causes 2. Any of the following atrial conditions: 
 • Left atrial anteroposterior diameter ≥ 5.5 cm (by MRI, CT or transthoracic echocardiography [TTE]*) • Any prior atrial endocardial or epicardial ablation procedure, other than right sided CTI ablation or for right sided supraventricular tachycardia • Any prior atrial surgery • Intra-atrial septal patch or interatrial shunt • Atrial myxoma • Current left atrium (LA) thrombus[#] • LA appendage closure, device or occlusion, past or anticipated • Any PV abnormality, stenosis or stenting (common and middle PVs are admissible)[¥] 3. At any time, one or more of the following cardiovascular procedures, implants or conditions:

	
• Sustained ventricular tachycardia or any ventricular fibrillation• Hemodynamically significant valvular disease:
a) Valvular disease that is symptomaticb) Valvular disease causing or exacerbating congestive heart failurec) Aortic stenosis: if already characterized, valve area < 1.5 cm² or gradient > 20 mmHgd) Mitral stenosis: if already characterized, valve area < 1.5 cm² or gradient > 5 mmHge) Aortic or mitral regurgitation associated with abnormal LV function or hemodynamic measurements• Hypertrophic cardiomyopathy• Any prosthetic heart valve, ring or repair including balloon aortic valvuloplasty• Pacemaker, implantable cardioverter defibrillator or cardiac resynchronization therapy devices• Any inferior vena cava (IVC) filter, known inability to obtain vascular access or other contraindication to femoral access• History of rheumatic fever• History of congenital heart disease with any residual anatomic or conduction abnormality 
4. Any of the following procedures, implants or conditions:
 
• At baseline or assessment before the procedure:
a) New York Heart Association (NYHA) Class III/IVb) Left ventricular ejection fraction (LVEF) < 40%c) Symptomatic hypotension or Uncontrolled hypertension (Systolic blood pressure > 160 mmHg or Diastolic blood pressure > 95 mmHg on two blood pressure measurements at baseline assessment)d) Symptomatic resting bradycardiae) Implantable loop recorder or insertable cardiac monitor• Within the 3 months preceding the procedure:
--	---

	
 a) Myocardial infarction or Unstable angina or Percutaneous coronary intervention b) Heart failure hospitalization c) Treatment with amiodarone d) Pericarditis or symptomatic pericardial effusion e) Gastrointestinal bleeding 
 • Within the 6 months preceding the procedure: 
 a) Heart surgery b) Stroke, TIA or intracranial bleeding c) Any thromboembolic event d) Carotid stenting or endarterectomy 
 5. Diagnosed disorder of blood clotting or bleeding diathesis 6. Subject who is not on anticoagulation therapy for at least 3 weeks prior to the ablation procedure 7. Medical conditions assessed before the procedure that would prevent participation in the study, interfere with assessment or therapy, significantly raise the risk of study participation, or modify outcome data or its interpretation, including but not limited to: 
 • Body Mass Index (BMI) $> 40.0 \text{ kg/m}^2$ • Solid organ or hematologic transplant, or currently being evaluated for an organ transplant • Severe lung disease, pulmonary hypertension, or any lung disease involving abnormal blood gases or requiring supplemental oxygen • Renal insufficiency with an estimated glomerular filtration rate (eGFR) $< 30 \text{ mL/min/1.73 m}^2$, or any history of renal dialysis or renal transplant • Active malignancy or history of treated malignancy within 24 months of enrollment (other than cutaneous basal cell or squamous cell carcinoma) • Clinically significant gastrointestinal problems involving the esophagus or stomach including severe or erosive esophagitis, uncontrolled gastric reflux, gastroparesis, esophageal candidiasis or active gastroduodenal ulceration • Active systemic infection • COVID-19 disease 
 a) Current confirmed, active COVID-19 disease
--	---

	
b) Current positive test for SARS-CoV-2c) Confirmed COVID-19 disease not clinically resolved at least 3 months prior to the procedure• Other uncontrolled medical conditions that may modify device effect or increase risk, including uncontrolled diabetes mellitus (HgbA1c > 8.0% if test result already obtained), untreated obstructive sleep apnea or active alcohol abuse8. Clinically significant psychological condition that in the Investigator's opinion would prohibit the subject's ability to meet the protocol requirements9. Employees/family members of:
• Boston Scientific or any of its affiliates or contractors• The Investigator, sub-Investigators, or their medical office or practice, or healthcare organizations at which study procedures may be performed10. Subjects known to require or have accepted ablation outside the PV region during the procedure except CTI region ablation.
--	--

**TTE obtained ≤ 6 months prior to procedure will be acceptable, unless a cardiac event has occurred (e.g. MI, acute heart failure or acute onset heart failure) between the date of the exam and the procedure. In this case, a new TTE is needed to confirm eligibility for mITT. The most recent report before the procedure will be used. LA anteroposterior diameter measured by M-mode from the parasternal long-axis view will be used.*

#The absence of thrombus must be confirmed by means of a trans-esophageal echocardiogram (TEE) within 48 hours prior to the procedure or Intracardiac Echography (ICE) during the procedure.

^Y Cardiac CT/MRI obtained ≤ 3 months prior to procedure will be acceptable.

9. Subject Accountability

9.1. Point of Enrollment

Subjects satisfied with all the key criteria will be considered enrolled into the clinical study at the time of the study-specific ICF execution. No data collection of study-related testing, procedures, etc. can take place until the ICF is signed and dated by the subject.

It is the investigative site's responsibility to assess eligibility criteria before obtaining the ICF and to document them for each screened patient in the study Screening and Enrollment Log. It is the responsibility of the delegated physician investigator to assess final eligibility criteria prior to data collection. If the subject is found to be ineligible prior to data collection, it must be documented.

9.2. *Withdrawal*

All subjects enrolled in the clinical study (including those withdrawn from the clinical study) shall be accounted for and documented. If a subject withdraws from the clinical investigation, the reason(s) shall be reported. If such withdrawal is due to problems related to device safety or performance, the investigator shall ask for the subject's permission to follow his/her status/condition outside of the clinical study.

Reasons for withdrawal include but are not limited to physician discretion, subject choice to withdraw consent, lost to follow-up or death. While study withdrawal is discouraged, subjects may voluntarily withdraw from the study at any time, with or without reason, and without prejudice to further treatment. In the event a subject decides to withdraw from the study, or an investigator withdraws a subject due to investigator discretion, every effort should be made to obtain full information on any on-going reportable Adverse Events/Serious Adverse Events up to the point of withdrawal. Additional data may no longer be collected after the point at which the subject has been withdrawn from the study or withdraws his/her consent, for whatever reason. Data collected up to the point of subject withdrawal may be used for study analysis, unless local regulations apply which require removal of the data. All applicable, electronic case report forms (eCRFs) up to the point of subject withdrawal and a "Subject End of Study" form (or equivalent) must be completed.

If the withdrawal is due to the investigator's discretion, the investigator is obligated to follow all open reportable Adverse Events until they can be considered as closed or chronic.

9.3. *Lost to Follow-Up*

A participant will be considered lost to follow-up if he/she fails to complete the routine follow-up visits scheduled visits and is unable to be contacted by the study site staff.

The following actions must be taken if a participant fails to return to the clinic for a required standard of care visit:

- The site will attempt to contact the participant and reschedule the missed visit and counsel the participant on the importance of maintaining the assigned visit schedule and ascertain if the participant wishes to and/or should continue in the study.
- Before a participant is deemed lost to follow-up, the investigator or designee will make every effort to regain contact with the participant (where possible, 3 telephone calls and, if necessary, a certified letter to the participant's last known mailing address or local equivalent methods). These contact attempts should be documented in the participant's medical record or study file.
- Should the participant continue to be unreachable, he or she will be considered to have withdrawn from the study with a primary reason of lost to follow-up.

9.4. *Subject Status and Classification*

As subjects are evaluated, enrolled and treated in the study, they will be grouped into one of the following four categories and analyzed by predefined sets. Categorization will help determine how data gathered from them will be stored and evaluated.

It is the investigational site's responsibility to list all screened subjects, Screening failure, INTENT, ATTEMPT and TREATMENT subjects on the Screening and Enrollment Log.

9.4.1. Screening Failure

A subject who has signed informed consent but is later determined to not meet key eligibility criteria will be classified as “Screening Failure”. Subjects not meeting key eligibility criteria due to oversight (i.e., I/E violation) will be considered ‘Screening Failure’. There are no follow-up reporting requirements for Screening Failure subjects. Subjects determined to be Screening Failure will not be used for analysis of the endpoints and do not count toward the enrollment ceiling. The original signed Informed Consent must be maintained in the site’s subject file. A subject Identification Number (ID) will be assigned in the EDC system.

For consent ineligible subjects the following forms must be completed:

- Enrollment and End of Study eCRF must be completed
 - Relevant eCRFs for study visits completed through consent ineligible determination, including device tracking, if applicable.
- Adverse Event forms for any reportable event, as defined in **Section 18.1** for any adverse event that occurs after signing the Informed Consent, up to the point of subject withdrawal

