Component Name	Model																																												
FARASTAR Pulsed Field Ablation Generator System																																													
FARASTAR Pulsed Field Ablation Generator	61M401																																												
FARASTAR Recording System Module (RSM)	61M407																																												
FARASTAR Stimulation Module Cable	61M404																																												
FARASTAR EGM Cable	61M405																																												
FARASTAR Stimulation Module Auxiliary Cable	61M408																																												
FARASTAR Cable Set	61M406																																												
FARASTAR Stimulation Module Male Cable	61M409																																												
FARASTAR Stimulation Module Female Cable	61M410																																												
FARASTAR Stimulation Module Y-Cable, Long	61M411																																												
FARASTAR Stimulation Module Y-Cable, Short	61M412																																												
FARASTAR Recording System Module Catheter Pin Cable	61M413																																												
FARASTAR Recording System Module ECG Trunk Cable	61M415																																												
FARASTAR Recording System Module ECG Output Module	61M416																																												
FARASTAR Recording System Module EGM Input Module	61M417																																												
FARAWAVE Pulsed Field Ablation Catheter																																													
FARAWAVE Pulsed Field Ablation Catheter, 35mm	41M402																																												
FARAWAVE Pulsed Field Ablation Catheter, 31mm	41M401																																												
FARASTAR Catheter Connection Cable	41M404																																												
FARADRIVE Steerable Sheath																																													
FARADRIVE Steerable Sheath	21M402																																												
Study Design	This is a retrospective and/or prospective single-center single-arm observational study.																																												

A Real-world Study of the FARAPULSE Pulsed Field Ablation System in A Chinese Population with Paroxysmal Atrial Fibrillation (REPLACE Study)

Planned Number of Subjects	At least 30 ATTEMPT and TREATMENT subjects
Planned Number of Sites / Countries	1 site

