9.4.2. INTENT

A subject who signs informed consent, meets key eligibility criteria, but does not have any study devices inserted into the body will be classified as “INTENT.” For prospectively enrolled subjects that are enrolled in the study but do not undergo ablation procedure within 30 days from consent signature date must not be reconsented and will be withdrawn from the study and classified as “INTENT.” These subjects won’t be allowed to be re-enrolled in the study.

There are no follow-up requirements for INTENT subjects. INTENT subjects will not count for analysis of the endpoints and do not count toward the enrollment ceiling. The original signed ICF must be maintained in the center’s patient file. A subject ID will be assigned in the EDC system.

For INTENT subjects, at the minimum the following forms must be completed:

- Enrollment and baseline forms such as, but not limited to informed consent, enrollment information and other related forms.
- End of Study form;
- Adverse Event forms for any reportable event, as defined in **Section 18.1** for any adverse event that occurs after signing the Informed Consent, up to the point of subject withdrawal

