9.4.3. ATTEMPT

An ATTEMPT subject is one who signs informed consent, meets eligibility criteria, and has any study device inserted into the body but does not receive ablation (PFA energy) with the FARAPULSE Pulsed Field Ablation System for PVI. ATTEMPT subjects will be used for analysis of the primary and secondary safety endpoints and count toward the enrollment ceiling.

The original signed Informed Consent and any relevant documentation must be maintained in the site’s subject file. A subject ID will be assigned in the EDC system. ATTEMPT subjects are not allowed to be re-enrolled in the study.

Prospectively enrolled ATTEMPT subjects will be followed up to 30 days for safety. For

retrospectively enrolled ATTEMPT subjects, one-month follow-up data will be collected. ATTEMPT subjects will not need to complete data collection of the post-procedure arrhythmia. All applicable eCRFs, per the protocol, will be completed.

For ATTEMPT subjects, at the minimum the following forms must be completed:

- Enrollment and baseline forms such as, but not limited to: ICF, enrollment information and other related forms.
- End of Study form.
- Protocol Deviation form
- Adverse Event forms for any reportable event, as defined in Section 18.1 for any adverse event that occurs after signing the ICF, up to the point of subject withdrawal

9.4.4. *TREATMENT*

Any subject that signs the ICF, meets key eligibility criteria and has the specified study device inserted into the body and receives PFA ablation with the FARAPULSE Pulsed Field Ablation system will be classified as “TREATMENT”. The data collection of these subjects will be performed in accordance with the follow-up schedule and are included in all study analyses. A subject ID will be assigned in the EDC system.

All applicable eCRFs, per the protocol, must be completed for TREATMENT subjects. TREATMENT subjects do count towards the enrollment ceiling and will be used for analyses of the endpoints. The original signed ICF and any relevant documentation must be maintained in the center’s patient file.

9.5. *End-of-Study Definition*

A clinical trial is considered completed when the last participant’s last study data collection has occurred.

A subject is considered to have completed the study if he/she has completed all data collection including the last visit or assessment as shown in the Data Collection Schedule shown in **Table 10-1**.

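### Protocol 9.4.1 sets no time limit on Screening Failure, so a device-exposed subject found late to fail a key criterion leaves the primary safety analysis (minor, cheap to close)

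*Protocol*

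**What the plan says.** - **Who becomes a Screening Failure (Protocol 9.4.1).** A consented subject who later proves not to meet the key criteria. Errors are covered too: "Subjects not meeting key eligibility criteria due to oversight (i.e., I/E violation) will be considered" Screening Failures.
- **Consequence (9.4.1).** "Subjects determined to be Screening Failure will not be used for analysis of the endpoints and do not count toward the enrollment ceiling". Also: "There are no follow-up reporting requirements for Screening Failure subjects".
- **Data still due (9.4.1).** Enrollment and End of Study eCRFs, forms for reportable adverse events after consent, and "Relevant eCRFs for study visits completed through consent ineligible determination, including device tracking, if applicable".
- **Exclusion rule (8.3).** A subject who meets a key exclusion criterion "cannot be included in this study or will be excluded from this clinical study", with no time stated.
- **The neighbouring class does have a device limit (9.4.2).** An INTENT subject is an eligible one who "does not have any study devices inserted into the body will be classified as" INTENT.
- **The analysed classes require eligibility.** ATTEMPT (9.4.3) is a subject who "meets eligibility criteria, and has any study device inserted into the body" without receiving energy. TREATMENT (9.4.4) and the ITT set (11.2.1; SAP 4.1) require the key criteria.
- **Populations.** Primary safety uses ATTEMPT and TREATMENT subjects within ITT. Per-subject acute procedural success uses TREATMENT subjects within mITT only (11.1.1.2.3, 11.2.1; SAP 3.1.3, 4.1). The secondary effectiveness endpoints use both ITT and mITT.
- **Planned number (Synopsis).** "At least 30 ATTEMPT and TREATMENT subjects".

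**The concern.** A safety rate is normally read as the rate among people in whom the device was used. Here a subject can have the device inserted, be followed through the 7-day window, and then be removed because a key criterion turns out not to have been met. By then the event status may be known. For retrospective subjects, whose procedure may precede consent, it may be known from routine care before the study judges eligibility. The removed subject does not count toward the planned number, so another takes the place and the denominator gives no sign of the removal.

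Adverse events reported after consent are still recorded, but outside the endpoint. If a retrospective subject consents after the 7-day window has passed, that reporting duty may not reach an event within the window.

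With about 30 subjects, and data meant to support registration in China (Protocol 7.3), one subject can decide whether the report shows no events or one.

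Only key criteria matter for this. Failing an additional criterion affects mITT membership, not the safety analysis.

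**Working it through.** **1. Can another analysis set recover the subject?**

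| Class or set | Eligibility required? | Limited by device insertion? | In primary safety? |
|---|---|---|---|
| Screening Failure (9.4.1) | no, fails a key criterion | no limit stated | no |
| INTENT (9.4.2) | yes | yes, no device inserted | no |
| ATTEMPT (9.4.3) | yes | device inserted, no energy | yes, within ITT |
| TREATMENT (9.4.4) | yes | device inserted, energy given | yes, within ITT |
| ITT (11.2.1; SAP 4.1) | yes | no | frame for the above |

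A device-exposed subject who fails a key criterion fits only the first row. The SAP defines no as-treated or all-exposed set.

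**2. The plan's own figures.** The exact (Clopper-Pearson) 95% interval for x events in n has lower limit = 2.5% quantile of Beta(x, n − x + 1) and upper limit = 97.5% quantile of Beta(x + 1, n − x). For n = 30:
- 0 events: 0 to 11.6%
- 1 event: 0.1 to 17.2%
- 2 events: 0.8 to 22.1%
- 3 events: 2.1 to 26.5%

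All four rows of the plan's table (Protocol 11.1.1.1.2; SAP 3.2.2) reproduce.

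**3. Effect of removing one exposed subject.** A Screening Failure is not counted, so assume 30 others are analysed. Keeping the subject gives n = 31.
- The removed subject had the only event: reported 0/30 = 0% (0 to 11.6%); with the subject kept, 1/31 = 3.2% (0.1 to 16.7%).
- The removed subject had no event and one other subject did: reported 1/30 = 3.3% (0.1 to 17.2%); kept, 1/31 = 3.2% (0.1 to 16.7%). This is the opposite direction.
- The Synopsis figure is a minimum. With 40 others counted (assumption), the first case becomes 0/40 (0 to 8.8%) against 1/41 = 2.4% (0.1 to 12.9%).

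**4. How likely is the first case?** The documents give no number of late violations. Given one, the pooled rate in Protocol 4.1.3 is 3/121 = 2.5% (exact 95% CI 0.5 to 7.1%). If it applied here, a removed subject would have had an event with probability of about 1 in 40. That is an assumption, because the earlier endpoint definitions and windows (7 or 30 days) differ.

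**5. Lesser point, acute success.** Assume 6 of 30 treated subjects fall outside mITT.
- All succeed: mITT 24/24 (85.8 to 100%); all treated 30/30 (88.4 to 100%).
- One failure inside mITT: 23/24 = 95.8% (78.9 to 99.9%) against 29/30 = 96.7% (82.8 to 99.9%).
- One failure in a subject outside mITT: 24/24 against 29/30. Only here does mITT show no failure although one occurred.

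**The case against.** **Eligible-only safety sets follow the programme's pattern.** Protocol 4.1.3 describes the ADVENT and consolidated PEFCAT safety sets as limited to eligible subjects, and ADVENT data may serve as a Bayesian prior here. This stands as a reason to show the rate in key-eligible subjects as well. It does not justify a removal rule with no time limit.

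**Eligibility is checked early.** Protocol 9.1 and 10.3 require it before data collection, and 10.4 and 10.5 place it at the Baseline Visit, before the procedure. The key criteria are few, and Screening Failures are entered on the Screening and Enrollment Log. This makes a late finding unlikely. It does not say what happens when one occurs, whereas 9.4.1 does: the subject is removed.

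**A cut-off at device insertion cannot serve everyone.** This stands. Retrospective subjects may already have been treated at consent, and 9.1 provides for finding a subject ineligible before data collection. They need a different cut-off.

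**A contradiction that a reader might infer.** Protocol 7 and 7.1 and SAP 2 promise 12 months of follow-up to everyone treated with the device, which seems to clash with 9.4.1. The definitions do not support that reading. Enrollment in 9.1 presupposes the key criteria, and 10.13 ties the 12-month visit to TREATMENT subjects, who must meet them. At most the wording could be aligned.

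**Device tracking.** The mention of it in 9.4.1 is qualified as applying only where relevant. It is compatible with a determination after device use but does not show that one was intended.

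**The mITT restriction has a stated reason,** similarity to ADVENT (Protocol 7.4), and ITT already has per-vein isolation and chronic success. This stands, so mITT should remain primary. Those ITT summaries show per-subject acute failure only in part.

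**Conclusion.** The gap is real but small. As written, a key-criterion violation found after exposure removes the subject from primary safety, with no follow-up reporting required and no other set to recover the subject. The illustrated effect, 0/30 in place of 1/31, needs three things together: a late violation, an event in that subject, and no event in anyone else. The plan has no hypothesis or performance threshold that the change could cross, and the two intervals overlap widely.

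Two stronger readings should be resisted. One is that the rule biases the safety rate downward. It does so only if removed subjects have more events than those kept, and step 3 shows the other direction too. The other is that mITT hides acute failures. Additional criterion 10 concerns ablation outside the pulmonary vein region. A failed isolation completed with another device (10.5.1.4) stays in mITT unless the subject also meets an additional exclusion criterion.

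Severity: minor, a cheap improvement. The text of the rule is certain. Its frequency is unknown, and the numbers rest on the assumptions stated with them.

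**What to change.** 1. **Prospective subjects.** Limit Screening Failure to those with no study device inserted. Keep device-exposed subjects with valid consent in the primary safety analysis and in the follow-up of their class (ATTEMPT or TREATMENT), and record the violation as a protocol deviation.
2. **Retrospective subjects.** Allow Screening Failure only until a dated eligibility decision in the existing Screening and Enrollment Log, made before outcome data are collected. Violations found after that date stay in the safety analysis as deviations.
3. **Transparency.** List every device-exposed subject who is excluded, with reason, timing and any known events. Show the safety rate restricted to key-eligible subjects as a sensitivity analysis, for comparability with the earlier studies.
4. **Acute success.** Keep mITT as the primary effectiveness set and add one table of per-subject acute procedural success in all TREATMENT subjects (ITT). Isolation is already collected for each vein (Protocol 10.5.2), so no new data are needed.

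**Cost.** Wording changes in Protocol 9.4.1, 9.4.3, 9.4.4 and 11.2.1 and SAP 4.1, one dated log entry per retrospective subject, a listing, and one or two extra tables. The downside is that a few ineligible subjects enter the safety denominator and must be followed. If enrollment is complete, items 3 and 4 can still be added through the route for changed analyses in Protocol 11.3.7 and SAP 5.5.
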